The latest findings from the Global Burden of Disease study indicate that China experiences 3.94 million new stroke cases annually, with a total of 28.76 million stroke patients, and 2.19 million stroke-related deaths each year [1]. Stroke is the third leading cause of death [2] and the primary cause of years lived with disability in China [1]. Among different subtypes of stroke, ischemic stroke accounts for the highest proportion, constituting 86% of stroke cases in individuals aged 40 and above [3], thereby placing a significant burden on both families and society.

Endovascular thrombectomy is one of the primary treatments for acute ischemic stroke due to large artery occlusion [2,3]. For acute anterior circulation large artery occlusion stroke, approximately 78%-96% of patients can achieve vessel recanalization through endovascular thrombectomy [4-8]. However, vessel recanalization does not equate to a good prognosis. The DIRECT-MT study found that the recanalization rates for direct thrombectomy and thrombectomy after intravenous thrombolysis within 4.5 hours of onset are 79.4% and 84.5%, respectively, while the good functional outcome rates are only 36.4% and 36.8% [5]. This mismatch suggests that solely pursuing vessel recanalization is insufficient to significantly improve clinical outcomes for stroke patients. Therefore, further researches on strategies to alleviate ischemia-reperfusion injury, based on vessel recanalization, holds the potential to overcome challenges in this field and provide new perspectives for the treatment of acute anterior circulation large artery occlusion stroke.

Blood pressure is a critical clinical management parameter that is closely linked to the prognosis of stroke patients. Observational studies suggest that elevated blood pressure is associated with worse functional outcome at 3 months in acute ischemic stroke patients undergoing thrombectomy [9-13]. Recent meta-analyses have demonstrated that high 24-hour mean systolic blood pressure following mechanical thrombectomy is correlated with both 3-month functional impairment and mortality [14, 15]. Currently, several randomized controlled trials have been conducted to investigate the optimal blood pressure management targets following intravascular therapy in patients with anterior circulation stroke. The results of the BP TARGET study [16] indicated that a greater reduction in systolic blood pressure within 24 hours following endovascular treatment was associated with better prognosis. However, no significant difference in 3-month outcomes was observed between the intensive SBP target group (systolic blood pressure between 100-129 mmHg

within 24 hours after successful endovascular therapy) and the standard SBP target group (systolic blood pressure between 130-185 mmHg within 24 hours after successful endovascular therapy). In this study, the difference in blood pressure between the intensified hypotension and standard blood pressure groups was relatively modest (average systolic blood pressure within 24 hours was 128 mmHg and 138 mmHg, respectively), which may have been insufficient to detect the potential benefits of a further reduction in systolic blood pressure. On this basis, the ENCHANTED2/MT study [17] employed a grouping strategy with more pronounced differences in blood pressure and found that, compared to the less intensive treatment group (systolic blood pressure between 140-180 mmHg within 72 hours), the more intensive treatment group (systolic blood pressure <120 mmHg within 72 hours) exhibited a higher proportion of poor functional outcome at 3 months. However, no significant differences were observed between the two groups in terms of symptomatic intracranial hemorrhage or 3-month mortality [17]. The recently published OPTIMAL-BP study [18] reached a conclusion consistent with that of the ENCHANTED2/MT study: the three-month poor functional outcome rate in the intensive management group (systolic blood pressure <140 mmHg within 24 hours) was significantly higher than that in the conventional management group (systolic blood pressure between 140-180 mmHg within 24 hours). Additionally, no significant differences were observed in the incidence of symptomatic intracranial hemorrhage or in the three-month stroke-related mortality between the two groups. The results of the BEST-II study [19], published almost simultaneously, demonstrated that lower SBP targets less than either 140mmHg or 160mmHg after successful endovascular therapy did not meet prespecified criteria for futility compared with an SBP target of 180mmHg or less. Therefore, it cannot be concluded that lower postoperative blood pressure targets are harmful [19]. In summary, existing studies present inconsistent recommendations regarding blood pressure management following successful reperfusion with endovascular thrombectomy, likely due to differences in populations, interventions, and other factors. Further precise researches are necessary to better define the optimal strategy.

The aforementioned randomized controlled trials did not fully account for the impact of stroke etiology on the results. Atherosclerosis and embolism are the two most common causes of acute ischemic stroke [20]. Patients with large large-artery atherosclerotic stroke often have long-term atherosclerotic stenosis of vessels, which promotes collateral circulation, resulting in better

collateral circulation compared to embolic stroke patients [21-23]. Studies have indicated that blood pressure variability following vascular recanalization is linked to prognosis in patients with poor collateral circulation, but not in those with good collateral circulation [24-26]. Thus, patients with embolic strokes may be more susceptible to the effects of blood pressure. A recent study confirmed this view by analyzing blood pressure data from 147 patients with atherosclerotic stroke and 273 patients with cardioembolic stroke [27]. The study found that in patients with cardioembolic stroke, greater blood pressure variability within 24 hours after endovascular therapy was associated with a lower risk of functional independence at 3 months and a higher risk of cerebral hemorrhage. However, these correlations were not observed in patients with atherosclerotic stroke [27]. After acute ischemic stroke, impaired cerebral autoregulation makes blood flow in penumbra highly sensitive to blood pressure [28]. Elevated blood pressure can increase cerebral perfusion pressure and induce microvascular dilation, which may trigger microvascular spasm, further damage the blood-brain barrier, and convert ischemic vessels into channels for cerebral edema and hemorrhagic transformation [15, 29]. Conversely, excessively low blood pressure can result in inadequate cerebral blood flow, causing hypoperfusion, enlarging the infarct, and contributing to a poor prognosis [30]. After endovascular thrombectomy, patients with large-artery atherosclerotic stroke often have residual stenosis. Intensive blood pressure control in these patients may lead to hypoperfusion and exacerbate ischemic symptoms, thus blood pressure should be maintained at a relatively higher level. In contrast, for patients with embolic stroke, as there is no residual stenosis in the vessels, the primary concern after vascular recanalization is preventing hyperperfusion-related hemorrhagic transformation, and blood pressure should be kept at a relatively lower level. Compared to patients with large artery atherosclerotic stroke, those with embolic stroke may require more stringent blood pressure management. Previous studies that directly pooled patients with different stroke etiologies may have masked the impact of blood pressure on prognosis.

Therefore, we proposed a multicenter randomized controlled trial to investigate the impact of early intensive blood pressure control on the prognosis of patients with embolic stroke after successful reperfusion following endovascular thrombectomy.

2. Objectives

To investigate the safety and efficacy of intensive blood pressure control after successful

reperfusion following thrombectomy in patients with acute anterior circulation large artery embolic stroke.

3. Design

The study employs a multicenter, prospective, randomized, endpoint-blinded, parallel-controlled trial design. Patients with acute anterior circulation large artery occlusive stroke, who receive successful reperfusion after endovascular thrombectomy within 4.5 or 6.0 hours of onset, without significant in-situ or proximal vessel stenosis, and with sustained elevated systolic blood pressure (≥ 140 mmHg for >10 minutes), will be enrolled according to the clinical inclusion and exclusion criteria. The enrolled patients will be randomly assigned to the experimental group or control group (1:1). The experimental group will undergo intensive blood pressure management (target systolic pressure <120 mmHg, achieved and maintained within 1 hour for 48 hours), while the control group will have less intensive blood pressure control (target systolic pressure 140-180 mmHg). Patients will be followed up for 3 months to assess their prognosis.

4. Patient selection

4.1 Inclusion criteria

Age ≥ 18 years;

To receive endovascular thrombectomy <24 hours after the onset of symptoms;

Diagnosed with acute anterior circulation ischemic stroke;

National Institutes of Health Stroke Scale (NIHSS) score ≤ 30 ;

Alberta Stroke Program Early CT Score (ASPECTS) ≥ 6 ;

Computed Tomography Angiography (CTA), Magnetic Resonance Angiography (MRA), or Digital Subtraction Angiography (DSA) confirming occlusion of the intracranial internal carotid artery or M1/M2 segment of the middle cerebral artery;

Successful recanalization of the occluded vessel without in-situ or proximal stenosis (modified Treatment in Cerebral Infarction, mTICI $\geq 2b$);

Sustained elevated systolic blood pressure (≥ 140 mmHg for at least two consecutive measurements, separated by >10 minutes) within 3 hours of reperfusion;

Written informed consent provided by the patient or their legal representative.

4.2 Exclusion criteria

Pre-existing stroke disability defined by a modified Rankin score (mRS) >2;

Unlikely to benefit from or tolerate endovascular thrombectomy, such as severe allergic reaction to contrast agents;

Failure to achieve mTICI \geq 2b with endovascular intervention, or presence of in situ or proximal vascular stenosis;

Patients with contraindications for the use of antihypertensive medications, such as allergy to components;

Intracranial space-occupying lesions, including brain tumors and vascular malformations;

Patients with severe liver or renal dysfunction, or those receiving dialysis (severe liver dysfunction is defined as alanine aminotransferase [ALT] $>$ 3 times the upper limit of normal or aspartate aminotransferase [AST] $>$ 3 times the upper limit of normal; severe renal dysfunction is defined as serum creatinine $>$ 3.0 mg/dL [265.2 μ mol/L] or glomerular filtration rate [GFR] $<$ 30 mL/min/1.73 m 2);

Serious illness with life expectancy $<$ 6 months;

Lactating women;

Participation in other interventional clinical trials within the past 3 months;

Any other conditions that render patients unsuitable for participation in this study or unable to complete the study process, such as psychiatric disorders, cognitive or emotional impairments, or physical conditions that hinder compliance with study procedures and follow-up.

4.3 Criteria for withdrawal

The study should be terminated if any of the following conditions occur:

Voluntary withdrawal, participants can freely withdraw at any time;

Deliberate or inadvertent non-compliance with the study procedures;

Any other circumstances where the investigator deems that continuing the study would harm the patient's health;

Patients can withdraw from the study at any stage for any reason. Similarly, the investigators have the right to terminate a patient's participation in case of an emergency medical condition. For patients who withdraw, the investigator must inquire about the reason for withdrawal and whether any adverse events (AE) occurred. If the withdrawal is due to an AE, follow-up should be conducted

until the AE is resolved, unless the investigators deem that the condition is due to the patient's underlying disease and is unlikely to resolve. The reason for withdrawal and the date must be recorded in the case report form (CRF).

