Blood pressure will be continuously monitored using a noninvasive device applied to the nonparalyzed arm or the right arm. The measurement intervals are as follows: every 15 minutes within the first hour post-randomization, every hour from 2 to 6 hours, every 6 hours from 4 to 24 hours, and then twice daily until day 7 (if the patient is discharged or dies before day 7, monitoring will be discontinued).

Given the clinical uncertainties regarding the potential benefits and risks, this study encourages adherence to the protocol but allows for adjustments to the treatment plan based on clinical needs. Nicardipine is recommended for blood pressure management, but other antihypertensive medications may be also selected according to the clinician's judgment.

Nicardipine injection administration protocol: dilute with saline or 5% glucose injection to prepare a solution containing 0.01–0.02% nicardipine hydrochloride (0.1–0.2 mg per 1 mL). Administer by intravenous infusion, starting at a rate of 2–10 μ g/kg body weight per minute. Once the target blood pressure is achieved, adjust the infusion rate while continuously monitoring blood pressure. If necessary, intravenous administration can be increased to a dose of 10–30 μ g/kg body weight per minute.

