8.1 Primary efficacy outcome

Functional independence (90-day mRS score ≤ 2).

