9.1 Statistical analysis populations

Intention-to-Treat (ITT) Population: This population will include all randomized patients, regardless of whether they receive the intended intervention. A modified ITT analysis will be conducted based on the principle of the closest approach to the ITT population. Patients who withdraw consent before the blood pressure intervention, do not undergo the assigned procedure after randomization, lack endpoint data, refuse follow-up, or are lost to follow-up will be excluded from the statistical analysis. The modified ITT analysis will be used to evaluate the effectiveness and safety of the treatment regimen.

Per-Protocol (PP) Population: This population will exclude all patients with significant protocol violations, such as those who are under 18 years of age, have a final diagnosis other than acute ischemic stroke, have sustained systolic blood pressure <140 mmHg post-surgery, do not achieve reperfusion (mTICI <2b), have a pre-stroke mRS score of 3-5, lack 3-month follow-up data, or do not achieve the expected blood pressure control. The PP analysis will serve as a supplement to the modified ITT analysis.

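### Section 4.3 ends participation for any non-compliance and requires no 90-day outcome afterwards, so randomised patients can leave the main analysis for post-randomisation reasons

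*Protocol*

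**What the plan says.** **Section 4.3 (Criteria for withdrawal)** opens with "The study should be terminated if any of the following conditions occur". Under that heading it can only mean the individual patient's participation. One listed condition is "Deliberate or inadvertent non-compliance with the study procedures". Section 4.3 gives no degree of severity, and inadvertent lapses count. For a withdrawn patient the investigator must ask the reason, ask about adverse events, and record reason and date. The only follow-up duty is conditional: "If the withdrawal is due to an AE, follow-up should be conducted", and it runs until the event resolves. Nothing requires the 90-day mRS or survival status.

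**Section 7 (Medication protocol)** says "this study encourages adherence to the protocol but allows for adjustments to the treatment plan based on clinical needs".

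**Section 8** sets the primary efficacy outcome, "Functional independence (90-day mRS score ≤ 2", and makes 3-month all-cause mortality a primary safety outcome. The pressure strategy itself covers about 48 hours (Sections 7.1 and 7.2).

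**Section 9.1** defines ITT as everyone randomised, whatever they received, and then adopts a modified version. Patients who "lack endpoint data, refuse follow-up, or are lost to follow-up will be excluded from the statistical analysis". The role of that set is plain: "The modified ITT analysis will be used to evaluate the effectiveness and safety of the treatment regimen". The per-protocol set separately removes patients who miss the expected pressure control and patients without 3-month data.

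**The concern.** Leaving the assigned strategy and leaving the trial are different events. The first is part of what a comparison of strategies should capture. The second destroys outcome data. Section 4.3 treats them as one. The intervention is over within days and the endpoint is at 90 days, so a departure from the strategy is no reason to stop collecting the outcome.

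The consequence is a chain. Non-compliance leads to termination, termination to no required 90-day assessment, and a missing assessment to exclusion from the main efficacy and safety analysis. Treatment is not blinded (only endpoint assessment is), and non-compliance is left undefined, so sites may apply the rule differently by arm. If those removed differ in prognosis and the removals differ by arm, the comparison is no longer protected by randomisation.

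This is a matter of trial conduct. A better analysis of missing data would not recover outcomes that sites had no duty to collect.

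**Working it through.** **1. The plan's own figure.** Inputs from Section 5: 35% control rate, a 10-point improvement (45%), two-sided 0.05, 80% power, 1:1.

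n = [1.960 × √(2 × 0.40 × 0.60) + 0.842 × √(0.35 × 0.65 + 0.45 × 0.55)]² / 0.10² = 375.6, so 376 per group. The stated 376 is reproduced.

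With 455 enrolled per group and the planned 20% loss, 455 × 0.80 = 364 remain, and power is 78.8%.

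**2. The passages side by side.**

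| Question | 4.3 | 7 | 9.1 |
|---|---|---|---|
| Does a departure from the strategy end participation? | Yes, if it is non-compliance; the term is not defined | Adjustment for clinical need is allowed | Missed pressure control is a per-protocol exclusion only |
| Is the 90-day outcome required afterwards? | No; only adverse-event follow-up | Not addressed | Not addressed |
| What if the outcome is absent? | Not addressed | Not addressed | Excluded from the modified ITT set |

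No passage says whether an adjustment under Section 7 is or is not non-compliance under 4.3.

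**3. Illustration of size.** Every input here except the 35% rate and the 364 per arm is an assumption. The true rate is 35% in both arms, so there is no effect. A share w of an arm is terminated, and a proportion p of those terminated would have been independent.

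- Rate among those retained = (0.35 − w × p) / (1 − w)
- Spurious difference d = retained rate (intensive) − retained rate (control)
- SE = √(2 × 0.35 × 0.65 / 364) = 0.03536, holding 364 per arm fixed for simplicity
- Two-sided type I error = Φ(−1.96 − d/SE) + 1 − Φ(1.96 − d/SE)

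| p | w intensive | w control | Retained, intensive | Retained, control | d (points) | Type I error |
|---|---|---|---|---|---|---|
| 20% | 5% | 5% | 35.8% | 35.8% | 0 | 5.0% |
| 20% | 5% | 2% | 35.8% | 35.3% | +0.5 | 5.2% |
| 20% | 15% | 5% | 37.6% | 35.8% | +1.9 | 8.2% |
| 20% | 15% | 2% | 37.6% | 35.3% | +2.3 | 10.2% |
| 10% | 5% | 5% | 36.3% | 36.3% | 0 | 5.0% |
| 10% | 5% | 2% | 36.3% | 35.5% | +0.8 | 5.6% |
| 10% | 15% | 5% | 39.4% | 36.3% | +3.1 | 14.1% |
| 10% | 15% | 2% | 39.4% | 35.5% | +3.9 | 19.7% |

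The most extreme row: (0.35 − 0.015)/0.85 = 0.3941 and (0.35 − 0.002)/0.98 = 0.3551, so d = 0.0390 and d/SE = 1.10.

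Across all combinations d runs from 0 to +3.9 points and type I error from 5.0 to 19.7%. If 30% of those removed would be independent, d stays below 0.8 points. If the termination rates are exchanged between arms, the sign of d reverses.

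**4. Balanced loss.** Even with no bias, removals beyond the planned 20% cost power. If total loss reached an assumed 25, 30 or 35%, power would be 76.1, 73.2 or 70.0%.

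**The case against.** There is a fair case against reading too much into 4.3, and much of it stands.

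- **Section 7 and 4.3 need not collide.** An adjustment the protocol permits is most naturally compliance with it. A reader might infer that any clinically justified change of strategy triggers termination. The text does not say so, though it draws no line either.
- **Section 9.1 points towards retention.** If missing the pressure target ended participation, a separate per-protocol exclusion for it would be largely redundant. The protocol seems to expect some off-target patients to reach 90 days. That narrows the problem, but it also shows that 9.1 and 4.3 do not fit together.
- **Collection after withdrawal is not forbidden.** A reader might infer that the 90-day outcome is certain to be lost. The documents support only that it is not required after a withdrawal unrelated to an adverse event. Section 4.4 defines dropout separately, as inability to complete the 3-month follow-up.
- **Direction is not established.** It is tempting to say that the lower target is harder to hold, so sicker intensive patients are removed and that arm is flattered. The protocol's figures do not settle this. The introduction reports a previous trial with 24-hour means of 128 mmHg (target 100–129) and 138 mmHg (target 130–185). The first suggests that below 120 is demanding; the second lies under this trial's control range of 140–180. Section 7.2 itself foresees control pressures falling below 140. Departures are plausible in both arms.
- **The harm runs through the 9.1 exclusion.** If that exclusion is raised as a separate point, the same bias should not be counted twice. What belongs to 4.3 is that it allows the outcome to go uncollected.

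What survives is a mandatory rule with no threshold, no duty to collect the outcome afterwards, and an analysis set that drops those without it.

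**Conclusion.** The point holds in limited form. Followed as written, 4.3 and 9.1 together let randomised patients leave the main analysis for reasons arising after randomisation that may be related to treatment, and 4.3 must be reconciled with Section 7 and with the per-protocol definition. This is more than a missing detail, because 4.3 states a rule.

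Neither the direction nor the size of bias can be derived from the protocol. The range of 0 to +3.9 points rests on assumed termination rates and on an assumed worse prognosis in those terminated. Its lower end is no bias at all, and its positive sign only reflects the assumption that intensive patients are terminated at least as often as control patients. It shows what could happen against a 10-point target difference and does not predict what will. The change is worth making while patients can still be followed, since uncollected outcomes may not be recoverable.

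**What to change.** In 4.3, remove non-compliance as a reason to end study participation. State that a patient who departs from the assigned strategy, for whatever reason, stays in the trial, with 90-day mRS and survival collected and analysed in the randomised arm, unless the patient withdraws consent to data collection. Make Section 7 and the analysis sets in 9.1 agree with that statement. No pressure target, treatment rule or sample size needs to change for this.

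Cost: a wording change to the protocol and completion of follow-up contacts already in the schedule of evaluations (Section 12). Label: cheap improvement.

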13.4 AEs reporting

Any AE occurring during the trial will be reported by the investigators and clinical sites to the relevant national and local regulatory authorities within the specified timeframes, in accordance with national regulations. The investigators will assist the regulatory authorities in investigating the AE and implementing appropriate corrective and preventive measures.

Any SAE occurring during the clinical study must be reported by the investigator to the study's ethics committee and the clinical research sponsor within 24 hours of becoming aware of the event. Additionally, the investigator must complete a serious adverse event form, documenting the time of occurrence, severity, duration, measures taken, and outcome.

The investigators should follow up and record the outcomes of all AEs, tracking patients who withdraw from the study due to an AE until the AE is fully resolved. The investigator must assess whether the AE is related to the study intervention and provide supporting evidence for this assessment. Any clinically significant abnormal findings in clinical or laboratory tests should be recorded on the adverse event form, with follow-up observations at least once a week until the condition normalizes or returns to baseline levels.

Researchers should follow up on all adverse events (AEs) to observe and record their outcomes, and track patients who withdraw from the study due to an AE until it is fully resolved. Researchers must assess whether the AE is related to the research intervention and provide supporting evidence for this assessment. All clinically significant abnormalities in clinical or laboratory tests should be documented in an AE form and monitored during follow-up, with observations conducted at least weekly until normal or baseline levels are restored.

14. Follow-up and medical measures after study completion

The patients will be followed up within 3 months after discharge and continue long-term secondary prevention treatment for cerebral infarction.

15. Data retention

The CRF is prepared in triplicate: one copy is retained by the sponsor, one by the participating institution, and one by the statistical unit. Demographic data, relevant medical history, physical examinations, laboratory test results, concomitant medications, and adverse events are recorded in the CRF as raw data, with any information related to the subject's privacy documented only in the original medical records.

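### Sections 4.3 and 13.4 conflict on following an adverse event that led to withdrawal, and with the Section 9.1 exclusion the 90-day outcomes of the sickest withdrawn patients can be lost

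*Protocol*

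**What the plan says.** Section 4.3 lists grounds for withdrawal that include the investigator's view that continuing would harm the patient, and adds that "the investigators have the right to terminate a patient's participation in case of an emergency medical condition". On what follows it says: "If the withdrawal is due to an AE, follow-up should be conducted" until the event has resolved, "unless the investigators deem that the condition is due to the patient's underlying disease and is unlikely to resolve".

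Section 13.4 covers the same patients. It says "The investigators should follow up and record the outcomes of all AEs" and, in the same sentence, "tracking patients who withdraw from the study due to an AE until the AE is fully resolved". A later paragraph repeats the duty: "track patients who withdraw from the study due to an AE until it is fully resolved". Neither statement has an exception.

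Section 9.1 defines the ITT population as everyone randomised, then assigns the evaluation of effectiveness and safety to a modified ITT analysis. In that analysis, patients who "lack endpoint data, refuse follow-up, or are lost to follow-up will be excluded from the statistical analysis". Section 4.4 classes anyone who does not complete the 3-month follow-up as a dropout.

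The primary efficacy outcome (Section 8.1) is mRS 2 or less at 90 days. All-cause mortality at 3 months is one of the primary safety outcomes (Section 8.2). The schedule in Section 12 places an mRS assessment in the follow-up phase but does not say whether it applies to patients who have been withdrawn.

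**The concern.** A site with an unresolved AE that it attributes to the underlying disease is excused from follow-up by Section 4.3 and held to it by Section 13.4. It cannot tell which rule applies.

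The exception also falls on a particular kind of patient. The underlying disease is the index stroke, and events such as symptomatic haemorrhage or herniation can be attributed to it and may not resolve. Sections 8.2 and 8.4 count these events as safety outcomes. A rule that relaxes follow-up for conditions thought unlikely to resolve therefore selects on poor prognosis.

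The decisions to withdraw and to attribute are made by investigators. Section 3 describes the design as endpoint-blinded, and Sections 7.1 and 7.2 have the treating team work to the assigned pressure target, so these decisions may be made knowing the arm. If more patients leave by this route in one arm, that arm loses mRS 3–6 outcomes and deaths, and both functional independence and mortality look better there than they are.

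**Working it through.** **The texts side by side, for a patient withdrawn because of an AE**

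| Situation | Section 4.3 | Section 13.4 | 90-day mRS and vital status |
|---|---|---|---|
| AE resolves before day 90 | AE follow-up ends at resolution | Same | Not stated |
| AE unresolved, not attributed to underlying disease | Follow to resolution | Same | Not stated |
| AE unresolved, attributed to underlying disease, unlikely to resolve | Waived | Follow to full resolution | Not stated |

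The sections conflict in the third row only. The last column is the same in every row: the protocol neither requires nor forbids collecting the 90-day outcome after withdrawal. If it is not collected, Section 9.1 removes the patient.

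**The plan's own figure**

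Inputs from Section 5: 35% vs 45%, two-sided alpha 0.05, power 80%, 1:1 allocation. With pooled variance and no continuity correction,

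n = [1.960 × √(2 × 0.40 × 0.60) + 0.842 × √(0.35 × 0.65 + 0.45 × 0.55)]² / 0.10² = (1.358 + 0.580)² / 0.01 ≈ 376 per group.

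This matches the protocol, and the point made here does not change it.

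**Size of the possible bias**

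Assumptions (the documents give no loss rate): functional independence is truly 35% in both arms, a share w of an arm is excluded, and every excluded patient has mRS above 2. The observed rate in that arm is then

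p_obs = 0.35 / (1 − w).

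- w = 2%: 0.35/0.98 = 35.7%
- w = 5%: 0.35/0.95 = 36.8%
- w = 10%: 0.35/0.90 = 38.9%

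The last column below is the probability that a two-sided pooled z test rejects at 0.05, with 455 randomised per arm (Section 5) before exclusions.

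| Loss, one arm vs the other | False difference (points) | Rejection under no true effect |
|---|---|---|
| 2% vs 0% | 0.7 | 5.6% |
| 5% vs 2% | 1.1 | 6.4% |
| 5% vs 0% | 1.8 | 8.8% |
| 10% vs 5% | 2.0 | 9.4% |
| 10% vs 0% | 3.9 | 22% |
| Equal loss | 0 | 5% (nominal) |

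Worked case, 5% vs 0%: the arms keep 455 and 455 × 0.95 = 432.25 patients, and the difference is d = 0.3684 − 0.35 = 0.0184. The pooled rate is 318.5/887.25 = 0.359, and the standard error is about 0.0322. The upper tail is 1 − Φ((1.960 × 0.0322 − 0.0184)/0.0322) = 0.083 and the lower tail is 0.006, which together give 8.8%.

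**Mortality, as an extreme case**

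Assume a true mortality of 15% (not in the documents), loss in one arm only, and every lost patient dead. Observed mortality becomes (15 − 3)/97 = 12.4% at 3% loss and (15 − 5)/95 = 10.5% at 5% loss. These cases hide 3/15 = 20% and 5/15 = 33% of that arm's deaths, so they are an upper illustration and not an expectation.

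**The case against.** A reader might infer that Section 4.3 itself ends follow-up at AE resolution, so that a patient withdrawn for herniation needs no 90-day assessment and the worst outcomes are bound to be lost. The text does not say that. The sentence sets how long an AE is followed after withdrawal. It mentions neither the 90-day mRS nor vital status, and it does not stop a site from obtaining them.

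Nor is the exception the main cause of any loss. Without it, an AE that resolves in the second week would still end AE follow-up long before day 90. The loss needs three things together: a withdrawal, no stated duty to collect the 90-day outcome, and the Section 9.1 exclusion. The exception makes this worse for the patients with the poorest outlook.

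It can also be said that the protocol treats haemorrhage, herniation and death as outcomes to be counted and does not list them as reasons for withdrawal, and that Section 7 lets treatment be adjusted without ending participation. That is fair. However, the wording about an emergency medical condition is broad enough to cover such events.

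Finally, one-sided loss in which every lost patient does badly is an extreme assumption, and at small imbalances the efficacy bias is modest against a 10-point target. That stands as a limit on the size, but nothing in the protocol makes the loss equal between arms. A statistical analysis plan could not repair this fully, because it cannot recover outcomes that sites were never required to collect.

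**Conclusion.** The contradiction between Sections 4.3 and 13.4 is plain on the text and must be reconciled. The consequence for the trial's results is conditional: 90-day mRS scores and deaths among the sickest withdrawn patients can be lost, and Section 9.1 would then remove those patients from the main analysis of effectiveness and safety. The documents do not show that this will happen, or how often.

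If it does, and the loss differs by arm, the false difference in functional independence is about 0.7 to 3.9 points for imbalances from 2% vs 0% to 10% vs 0%. This assumes a true 35% in both arms and that every lost patient has mRS above 2. Equal loss gives no bias under the null. Mortality would be biased in the same direction, by an amount that depends on a death rate the documents do not give. The change is worth making because the gap affects a primary efficacy and a primary safety outcome and costs little to close.

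**What to change.** 1. In Section 4.3, state that stopping the intervention, or withdrawal by the investigator, does not end outcome follow-up. Require 90-day mRS and vital status, by telephone or from records, for every randomised patient unless consent to follow-up is itself withdrawn.
2. In Section 9.1, state that these patients stay in the main analysis.
3. Give Sections 4.3 and 13.4 one common rule for following an AE after withdrawal, with a defined end that is not earlier than day 90. Simply deleting the exception, or following to the later of resolution and day 90, would leave permanent deficits with no end date.

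The cost is a short protocol amendment and a few extra 90-day contacts. The sample size is unaffected.
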